8.5.4. Morning Glucose Levels

Morning glucose levels will be summarized in a table and provided in the listings. Plots for individual patient profile of morning glucose level and overnight cornstarch dose will be presented by study day. Plots for individual patient profile of weekly mean morning glucose level and overnight cornstarch dose will also be presented.

8.6. Safety Analysis

The safety parameters will include AEs, SAEs, vital sign measurements, complete and targeted physical examination findings, electrocardiogram (ECG) results, documented symptomatic hypoglycemic events, clinical laboratory assessments (clinical chemistry [including liver function tests], hematology, coagulation panel, and urinalysis), vector shedding, vector genome determination, measurement of neutralizing antibody titer to AAV8, measurement of AAV8 binding antibody immunoglobulin G (IgG), assessment of any cell-mediated immune responses to AAV8 and G6Pase, and measurement of anti-G6Pase antibodies.

Except for the CRM modelling described above, all statistical analyses of safety outcomes will be descriptive.

8.6.1. Adverse Events

Adverse events will be coded by system organ class (SOC) and preferred term (PT) using the current version of Medical Dictionary for Regulatory Activities.

An AE (classified by preferred term) will be considered a treatment emergent adverse event (TEAE) if it occurs on or after the DTX401 dose and is not present prior to the DTX401 dose, or it is present at the DTX401 dose but increases in intensity, severity, or frequency during the study.

Subject incidence of AEs will be tabulated as the following:

- Summary of AEs
- TEAEs by SOC and PT
- DLTs by SOC and PT
- Related TEAEs by SOC and PT
- Serious TEAEs by SOC and PT
- Serious Related TEAEs by SOC and PT
- Grade 3 or 4 TEAEs by SOC and PT
- Fatal TEAEs by SOC and PT
- TEAEs leading to discontinuation of study by SOC and PT
- TEAEs by PT
- TEAEs by PT and greatest severity

Summary tables by SOC and PT will include number of subjects as well as number of events. Detailed listings for all AEs, DLT, TEAEs leading to the discontinuation of study, and death will also be generated.

The severity will be based on the most current version of CTCAE. If an AE cannot be graded based on CTCAE, the investigator will assign a severity based on 1 = mild, 2 = moderate, 3 = severe, 4 = life threatening, and 5 = death.

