hepatitis and treated with corticosteroids if needed (Section 8.2.6.2), having an interval of more than 14 days between subjects in Cohorts 1 and 2 and more than 7 days between subjects in subsequent cohorts does not change either safety evaluations or the medical management of study subjects. To date, no related serious adverse events (SAEs) or DLTs have been reported for DTX401. Consistent with previous experience (Manno et al., 2006; Nathwani et al., 2011b; Nathwani et al., 2014), mild, transient, asymptomatic increases in liver aminotransferase levels have been observed following DTX401 administration that resolved with steroids (Derks et al., 2019; Weinstein et al., 2019).

Subject safety will be closely monitored throughout the study, including assessment of hypoglycemic events, frequent monitoring of liver enzymes, and inpatient observation following dosing and at multiple time points throughout the 52-week study duration.

For Cohorts 1 and 2, there was a minimum of 12 weeks (84 days) between dosing of the last subject in a dosing cohort and the first subject in the next dosing cohort. After all subjects in Cohorts 1 and 2 completed Week 12, the continual reassessment method (CRM) proposed a dose for the next cohort using the collected data from the previous cohort. The DMC met to review safety data (ie, AEs/SAEs, physical examination findings, vital sign measurements, electrocardiogram [ECG] results, and clinical laboratory assessments [including assessment of liver function]) and provide a recommendation for progressing to the next dosing level (Section 9.3). The CRM will be used for dose escalation to estimate the maximum tolerated dose (MTD) of DTX401 (Section 10.2.1).

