**9.1.3. Assessment of Severity/Toxicity**

The severity/toxicity, or intensity, of an AE refers to the extent to which an AE affects the subject’s daily activities. The Investigator should rate the intensity of an AE as Grade 1, 2, 3, 4, or 5 based on their medical judgment. The most current version of the NCI CTCAE can be used to guide the rating of an AE.

The CTCAE provides descriptive terminology that can be used to standardize AE reporting. A severity/toxicity grade is provided for each AE term that is grouped by the highest level of MedDRA classification. Specific symptoms and medical conditions have a clinical description for each level of severity/toxicity.

Increases in liver aminotransferase levels following DTX401 administration that are considered related to vector-induced hepatitis are expected, transient, asymptomatic, and self-limiting based on available evidence. If considered clinically significant in the Investigator’s medical judgment (Section 8.2.6.2), these events should be recorded as an AE (Section 9.1.2.1) or SAE (Section 9.1.2.2) with an event term of elevated liver function tests and graded according to the general guidelines outlined in Table 4.

In the event that an AE occurs during the study that is not captured by the CTCAE, the AE should be graded according to the general guidelines outlined in Table 4.

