**Table 4: General Guidelines for Grading Events Not Captured by the CTCAE**

Grade	Criteria
Grade 1	Mild; asymptomatic or mild symptoms; clinical or diagnostic observations only; intervention not indicated.
Grade 2	Moderate; minimal, local, or noninvasive intervention indicated; limiting age-appropriate instrumental ADL. a
Grade 3	Severe or medically significant but not immediately life threatening; hospitalization or prolongation of hospitalization indicated; disabling; limiting self-care ADL. b
Grade 4	Life-threatening consequences; urgent intervention indicated.
Grade 5	Death related to AE.

Abbreviations: ADL = activities of daily living; AE = adverse event; CTCAE = Common Terminology Criteria for Adverse Events.

a Instrumental ADL refers to preparing meals, shopping for groceries or clothes, using the telephone, managing money, etc.

b Self-care ADL refers to bathing, dressing and undressing, feeding self, using the toilet, taking medications, and not bedridden.

Changes in the severity/toxicity of an AE should be documented to allow an assessment of the duration of the event at each level of intensity to be performed. Adverse events characterized as intermittent do not require documentation of onset and duration of each episode.

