### **10.2.2. Sample Size Justification**

Simulations (result on file at PPD) show that if all 3 doses are safe and no DLTs occur, the CRM will recommend dose escalation to  $1 \times 10^{13}$  GC/kg (genome copies measured by [REDACTED]) and the recruitment of 12 subjects. Based on safety and efficacy observations in Cohorts 1, 2, and 3 (3 subjects each) and a positive recommendation from the DMC, it was decided to enroll a fourth cohort of 3 subjects. The planned sample size of the study will therefore be 12 subjects including 4 cohorts.

The protocol allows multiple cohorts to be enrolled to assess varied oral steroid regimens to manage the mild, asymptomatic elevations in liver aminotransferase levels that have been observed following DTX401 administration (Derks et al., 2019; Weinstein et al., 2019). The CRM model will evaluate subjects based on the dose administered regardless of the steroid approach used (ie, reactive vs prophylactic).

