5.4. Dose-Limiting Toxicity

A DLT is defined as any AE/SAE ≥Grade 3 that is considered by the Investigator and/or Sponsor to be related to DTX401, based on the National Cancer Institute (NCI) Common Terminology Criteria for Adverse Events (CTCAE), the most recent version.

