8.6.7. Clinical Laboratory Assessments

Clinical laboratory assessments are mainly collected at central laboratory (Table 2), except for data collected during CFC which is collected at local laboratory and analyzed as described in Section 8.5.1. For all central clinical laboratory parameters (Table 2) with continuous results, absolute values and changes from baseline will be summarized by study visit. For central laboratory parameters with categorical results, results will be included in a listing because these parameters are either non-critical for analysis (e.g., Urinalysis blood (by dipstick), or microscopic examination parameters, etc.) or they are collected only at screening visit (e.g., HBV surface antigen).

Listings of laboratory parameters will be provided. Individual patient profile of triglyceride with daily cornstarch intake over time will be plotted.

Table 2: Central Clinical Laboratory Parameters

Clinical chemistry:	Lipid panel, uric acid, sodium, potassium, chloride, carbon dioxide, blood urea nitrogen, creatinine, glucose, calcium, phosphate, magnesium, albumin, total protein, creatine kinase, bilirubin (total, direct, and indirect), ALT, AST, ALP, gamma-glutamyl transferase, and lactate dehydrogenase
Hematology:	Complete blood count with differential
Urinalysis:	Specific gravity, pH, glucose, protein, blood (by dipstick), ketones (by dipstick), and microscopic examination (if blood or protein is found)
Other:	HBV surface antigen, HCV RNA, HIV,
(collected only at Screening)	
Coagulation panel:	PT/INR, aPTT
24-Hour urine:	Total protein, microalbumin, and creatinine

Abbreviations: ALP = alkaline phosphatase; ALT = alanine aminotransferase; aPTT = activated partial thromboplastin time; AST = aspartate aminotransferase; HBV = hepatitis B virus; HCV = hepatitis C virus; HIV = human immunodeficiency virus; PT/INR = prothrombin time/international normalized ratio.

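### Vector-related ALT rises are graded by Protocol Table 4, which has no ALT level, while AE severity in the SAP and DLTs in both documents are described as CTCAE-based

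*SAP*

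**What the plan says.** Several rules bear on how an ALT rise is graded and shown.

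- **Protocol 9.1.3.** Aminotransferase rises attributed to vector-induced hepatitis, if judged clinically significant, are recorded "with an event term of elevated liver function tests and graded according to the general guidelines outlined in Table 4". A separate paragraph then deals with the general case: "In the event that an AE occurs during the study that is not captured by the CTCAE". CTCAE otherwise serves as an optional guide to the investigator's rating.
- **Protocol Table 4.** The criteria are clinical and functional. Grade 1 reads "Mild; asymptomatic or mild symptoms; clinical or diagnostic observations only; intervention not indicated". No row mentions an enzyme level.
- **SAP 8.6.1.** "The severity will be based on the most current version of CTCAE", with an investigator-assigned 1 to 5 scale only when CTCAE cannot grade the event. Table 4 is not cited.
- **DLT definition.** SAP 5.4 counts related events of Grade 3 or more, "based on the National Cancer Institute (NCI) Common Terminology Criteria for Adverse Events (CTCAE), the most recent version". Protocol 9.1.1.1 also uses CTCAE. The enrollment stopping rule (Protocol 3.2.4, SAP 3.7) does too.
- **ALT outputs.** SAP 8.6.7 states: "For all central clinical laboratory parameters (Table 2) with continuous results, absolute values and changes from baseline will be summarized by study visit". It also plans laboratory listings, and SAP 8.6.7.1 plans individual plots of ALT with steroid dose.
- **Departures from the protocol.** SAP 9 declares none.

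**The concern.** AE incidence by severity and relationship, including DLTs, is the primary endpoint. The aminotransferase rise is the product-related event the protocol expects, and Protocol 10.2.2 says the design "allows multiple cohorts to be enrolled to assess varied oral steroid regimens" to manage it. This is therefore the event whose grade most needs a clear meaning.

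Under Table 4 an asymptomatic rise fits Grade 1, or Grade 2 if a short oral steroid course counts as the minimal intervention named there. Grade 3 depends on the investigator calling the event severe or medically significant, not on the ALT value. I assume that CTCAE grades such a rise by enzyme level; the documents do not reproduce its cut-offs. On that assumption a large but silent rise could be recorded as Grade 1 or 2 and still be Grade 3 or more on the scale that defines a DLT.

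Two things could then go wrong. A severity table described as CTCAE-based but filled with Table 4 grades would be read as showing small ALT rises. And a DLT count taken from recorded grades would miss an event that Protocol 9.1.1.1 counts, and that count feeds the continual reassessment model (CRM).

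**Working it through.** **Inputs.** From Appendix 2 of either document: doses d = 2, 6, 10 with reference 6; x = log(d/6); P(DLT) = exp(α + βx) / (1 + exp(α + βx)); α has mean −2.3097 and SD 1.6604; correlation −0.2405. The MTD is the highest dose with posterior mean P(DLT) at or below 0.25. Allocation: 3 subjects at Dose 1 (Cohort 1) and 3 + 3 + 3 = 9 at Dose 2 (Cohorts 2 to 4).

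The prior for log β is ambiguous. Appendix 2 gives log β a normal distribution with mean μ_β and SD σ_β, then reports values for log μ_β (−0.4323) and log σ_β (0.0044). Three readings were run:

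- A: mean −0.4323, SD 0.0044.
- B: mean −0.4323, SD exp(0.0044) = 1.0044.
- C: mean exp(−0.4323) = 0.649, SD 1.0044.

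**The plan's own figure.** The sample size sections say that with no DLTs the model escalates to Dose 3 and recruits 12. After 0/3 at Dose 1 and 0/3 at Dose 2, the Dose 3 posterior mean is 0.092 (A), 0.125 (B) and 0.279 (C). Under A and B the model escalates, and six subjects at Dose 3 meet a stopping rule: 3 + 3 + 6 = 12. Under C it stays at Dose 2. This favours A or B but does not settle the reading.

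**Effect of regrading.** Let k be the number of the nine Dose 2 subjects with a related rise that is Grade 3 or more by CTCAE but lower by Table 4, with 0/3 at Dose 1 and no other DLTs. The documents give no value for k; 0 to 4 is an assumed range. Posterior means are shown for Dose 2, then Dose 3.

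| k | A | MTD | B | MTD | C | MTD |
|---|---|---|---|---|---|---|
| 0 | 0.045, 0.060 | 3 | 0.045, 0.090 | 3 | 0.047, 0.231 | 3 |
| 1 | 0.101, 0.132 | 3 | 0.101, 0.171 | 3 | 0.107, 0.336 | 2 |
| 2 | 0.169, 0.217 | 3 | 0.170, 0.262 | 2 | 0.181, 0.440 | 2 |
| 3 | 0.243, 0.304 | 2 | 0.245, 0.354 | 2 | 0.262, 0.535 | 1 |
| 4 | 0.320, 0.390 | 1 | 0.323, 0.444 | 1 | 0.347, 0.621 | 1 |

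The Dose 1 mean stays below 0.25 throughout (at most 0.194, under A with k = 4).

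**Effect on incidence.** Each regraded subject moves Grade 3 or more incidence by 1/3 = 33 percentage points in a cohort and by 1/9 = 11 points at Dose 2.

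**Can the named outputs reconcile the scales?** By-visit summaries describe scheduled visits, not peaks. The listings and the plots follow ALT over time, but none is stated to show ALT against the upper limit of normal (ULN) or a laboratory grade. A reader could work out peaks by hand if reference ranges are printed. None of this says which grade is counted.

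**The case against.** The strongest reply is that only one grade exists. Protocol 9.1.2.1 collects the investigator's severity on the AE page, Protocol 9.1.3 rests it on medical judgment, and SAP 8.6.1 describes no regrading from laboratory values. The natural reading is that tables show the recorded grade. That stands, but it means SAP 8.6.1 misdescribes the scale for these events and the CTCAE-based DLT definition is not applied to them.

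A second reply is that Table 4 is titled for events CTCAE does not capture, so the SAP's fallback covers the case. This is arguable. However, Protocol 9.1.3 gives the liver rule and the rule for uncaptured events in separate paragraphs, and the fallback would still leave the DLT definition on CTCAE.

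Third, nothing suggests a large rise occurred. Protocol 1.3.1 reports that "mild, transient, asymptomatic increases in liver aminotransferase levels have been observed following DTX401 administration that resolved with steroids", with no DLTs or related serious events to date. SAP 3.7 reports no safety concerns from the data monitoring committee after review to Week 52 for Cohorts 1 to 3 and Week 24 for Cohort 4. That also stands, although the reports do not say which scale lies behind the word mild.

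Three stronger inferences are not supported:

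- **That the SAP departs from the Protocol on DLTs.** SAP 5.4 matches Protocol 9.1.1.1. Moving SAP 5.4 to Table 4 would create a new conflict.
- **That a set number of regraded subjects moves the MTD.** The threshold changes with the reading of the prior.
- **That ALT goes unreported.** Tables, listings and plots are planned, and the output shells are a separate document that was not available.

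**Conclusion.** The inconsistency is real and touches the primary endpoint. Protocol 9.1.3 pulls against Protocol 9.1.1.1, and SAP 8.6.1 omits the Table 4 exception. A reader might infer that a DLT has been missed or that the MTD estimate is wrong; no document shows either.

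The size depends on k. At k = 0, only the description of the severity scale is wrong. At k = 1 or more, Grade 3 or more incidence and the DLT count are understated, and for k = 0 to 4 the MTD estimate is Dose 3, 3, 3, 2, 1 (reading A), 3, 3, 2, 2, 1 (B) or 3, 2, 2, 1, 1 (C). These sequences are illustrative. They rest on the assumed range of k, on no other DLTs, and on CTCAE grading ALT by level. They would not change the planned cohorts, which are set at Dose 1 and Dose 2, but they would change the reported MTD and so the basis for the optimal biological dose.

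Two mismatches are minor. SAP 8.6.7.1 gives the steroid trigger as ALT above ULN, whereas Protocol 8.2.6.2.1 uses a rise from baseline or recent values. Protocol 10.2.4.6 includes local laboratory values in the analysis, whereas the SAP 8.6.7 summaries are for central values.

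**What to change.** 1. In SAP 8.6.1, state that the recorded investigator grade is tabulated, and that aminotransferase AEs attributed to vector-induced hepatitis carry the Table 4 grade. Footnote this on the severity table and the Grade 3 or 4 table. Leave SAP 5.4 on CTCAE, in line with Protocol 9.1.1.1.
2. Add one per-subject listing by cohort. It should show peak ALT as a multiple of ULN and of baseline (central and local results in separate columns), the study day of the peak, its CTCAE grade with the version stated, the recorded AE grade and causality, and prednisone exposure. Label it post hoc, because the data monitoring committee has already reviewed these data.
3. If any related rise in the 12-week DLT window is Grade 3 or more by CTCAE but was recorded lower, report the DLT count and the CRM estimate both ways, stating how the log β prior was entered.
4. As tidying, refer to the Protocol for the steroid trigger in SAP 8.6.7.1, and note in SAP 9 if local liver tests will not be summarized.

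The cost is SAP wording, two footnotes, one listing from data already collected, and at most one model rerun. No protocol change or new assessment is needed.

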8.6.2. Physical Examination

Physical examination date will be listed by study visit. Physical examination findings that are clinically significant per study investigator are documented and summarized as AEs.

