### **8.2.2. Physical Examination**

A complete or targeted physical examination will be performed at the time points specified in the Schedule of Events (Table 6).

A complete physical examination will include assessments of the head, eyes, ears, nose, and throat; skin; abdomen with documentation of liver and spleen size; and the endocrine, metabolic, neurological, respiratory, cardiovascular, gastrointestinal, and musculoskeletal systems.

A targeted physical examination will include assessment of the skin, the abdomen with documentation of liver and spleen size, and the respiratory, cardiovascular, and gastrointestinal systems.

Physical examination findings will be captured on the appropriate page of the eCRF.

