## **9. SAFETY MONITORING AND REPORTING**

### **9.1. Adverse Events and Serious Adverse Events**

Adverse events will be assessed from the time the subject signs the ICF and for up to 30 days after the End of Study/Early Withdrawal visit. SAEs that occur more than 30 days after the End of Study/Early Withdrawal visit need not be reported unless the Investigator considers them related to study product.

At every study visit, subjects will be asked a standard nonleading question to elicit any medically related changes in their well-being.

In addition to subject observations, AEs identified from any study data (eg, laboratory values, physical examination findings, ECG changes) or from review of other documents that are relevant to subject safety will be documented on the AE page in the eCRF.

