## **9.1.2. Safety Reporting**

### **9.1.2.1. Adverse Events**

All AEs reported or observed during the study will be recorded on the AE page in the eCRF. Information to be collected includes drug treatment, dose, event term, time of onset, Investigator-specified assessment of severity and relationship to study product, time of resolution of the event, seriousness, any required treatment or evaluations, and outcome. Adverse events resulting from concurrent illnesses, reactions to concurrent illnesses, reactions to concurrent medications, or progression of disease states must also be reported. All AEs will be followed to adequate resolution. The Medical Dictionary for Regulatory Activities (MedDRA) will be used to code all AEs.

Any medical condition that is present at the time that the subject is screened but does not deteriorate should not be reported as an AE. However, if the condition deteriorates at any time during the study, it should be recorded as an AE.

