#### **10.2.4.2. Physical Examination Findings**

Complete and targeted physical examination findings will be summarized by visit and dose.

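### SAP Section 9 declares no changes from the protocol, but SAP 8.6.2 drops the promised summary of physical examination findings and three lesser departures also go undeclared

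*SAP*

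**What the plan says.** Protocol 10.2.4.2 is a single commitment: "Complete and targeted physical examination findings will be summarized by visit and dose". The Safety Analyses paragraph of the Protocol Synopsis repeats that these findings will be summarized. SAP 8.6 agrees on their status: "The safety parameters will include AEs, SAEs, vital sign measurements, complete and targeted physical examination findings".

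The section that should deliver the output, SAP 8.6.2, has two sentences. The first is "Physical examination date will be listed by study visit". The second is "Physical examination findings that are clinically significant per study investigator are documented and summarized as AEs".

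On collection, Protocol 8.2.2 says "Physical examination findings will be captured on the appropriate page of the eCRF". It defines the content even of the shorter examination: "A targeted physical examination will include assessment of the skin, the abdomen with documentation of liver and spleen size", plus three body systems.

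SAP Section 9 is headed as the place for changes to protocol-specified analyses. Its whole entry is the word *None*. Protocol Section 10 says that the SAP will expand on the protocol's methods and that analyses may be added. It does not mention removing any.

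**The concern.** Safety is the primary objective of this first-in-human study. A reader who sees that Section 9 reports no changes will expect every safety output in Protocol 10.2.4 to be produced. Followed as written, SAP 8.6.2 yields examination dates and whatever became an AE. It gives no view of the findings themselves over time or by dose.

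Liver size is the clearest example. The Protocol Introduction names hepatomegaly as a complication of GSDIa, and the vector is directed at the liver. Liver and spleen size are documented at each examination. A change that the investigator does not consider clinically significant, or a reduction in liver size, would not be an AE and so would appear in no output that the SAP describes.

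The second stake is traceability. With Section 9 as it stands, a reader cannot tell a deliberate simplification from an oversight.

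**Working it through.** No arithmetic applies. The check sets each protocol commitment beside the SAP text that replaces it.

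| Output | Protocol commitment | SAP text | What changes | What remains |
|---|---|---|---|---|
| Physical examination | 10.2.4.2: findings summarized by visit and dose | 8.6.2: date listed; significant findings go to AEs | Summary of findings removed; as written, no listing of findings either | Clinically significant findings in the AE tables |
| Immune and vector parameters against dose | 10.2.4.7: association with dose to be examined in tables, with suitable methods set out in the SAP | 8.6.8: optional look at the listings | Firm commitment becomes optional; no method named | Summaries by visit, by cohort under the SAP 8.1 default |
| Categorical laboratory results | 10.2.4.6: shifts from Baseline by visit and cohort | 8.6.7: listing only | Shift tables removed | Listing, with a reason given in 8.6.7 |
| Symptomatic hypoglycemic events | 10.2.4.5: number of events by dose level | 8.6.6: number of subjects reporting events, by visit | Event counts become subject counts | Listing of event details |

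**Is the first row a typing error?** Possibly. If *date* is read as *data*, SAP 8.6.2 gives a listing of findings. That is better than dates, but it is still not a summary by visit and dose. The departure survives either reading.

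**Do neighboring sections show the same pattern?** No. SAP 8.6.3 summarizes and lists vital signs, 8.6.4 summarizes ECG shifts and lists results, 8.6.5 lists ultrasound results, and 8.6.6 lists event details. Only 8.6.2, as written, presents no result from the assessment that it covers.

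**Is any of the four declared elsewhere?** The SAP change history does not record any of them as a departure from the protocol. SAP 8.6.7 explains its own choice where it occurs, but Section 9 does not refer to it.

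**Can dose still be read from the tables?** Yes. Under SAP 8.1, tables are by dosing cohort and overall. Cohort 1 (3 subjects) received Dose 1, and Cohorts 2 to 4 (3 × 3 = 9 subjects) received Dose 2, so every cohort column identifies one dose. With 3 against 9 subjects, only description is possible in any case.

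**The case against.** The best reply is that little of consequence is lost. Clinically significant findings are summarized as AEs, by cohort. Protocol 9.1 requires AEs identified from examination findings to be recorded. For a condition already present at screening, Protocol 9.1.2.1 says "if the condition deteriorates at any time during the study, it should be recorded as an AE". What goes unsummarized is what the investigator did not consider significant, in about 12 subjects. The laboratory change is explained where it is made: screening-only tests cannot show a shift, and 24-hour urine protein is continuous and still summarized. For the vector parameters, the SAP adds peak value, time to peak, time to below detection and median shedding by cohort. The table shells, kept separately under SAP Section 10, might contain more than the text does.

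Most of this stands and sets the size of the point. It does not make the Section 9 entry true, and it does not restore the examination summary.

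Three stronger readings are tempting and are not supported:

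- *A reader might infer that examination safety data are lost altogether.* They are not: the AE route is intact.
- *A reader might infer that the immune and vector parameters are no longer tabulated by dose.* The by-visit, by-cohort tables already separate the doses. What weakened is the commitment to an association analysis and the naming of a method.
- *A reader might count the examinations affected by multiplying the current visit schedule by 12 subjects.* The amendment history shows that the Week 4, 6 and 36 examinations were added only in Version 7.0. That version already discusses Week 52 fasting data from Cohorts 2 and 3, so the product would be a ceiling that does not describe most earlier subjects.

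**Conclusion.** The point holds and is minor. SAP Section 9 is inaccurate. The departure that matters is SAP 8.6.2, where a promised by-visit, by-dose summary of a named safety parameter is replaced by dates, or at best a listing. The other three are lesser: a commitment softened without a named method, a change explained locally but not cross-referenced, and a change of counting unit for hypoglycemic events.

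The AE and DLT tables, the CRM and the sample size are unaffected, and no dose decision is shown to depend on the missing outputs.

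The conclusion concerns the SAP text and rests on two assumptions: that the text governs what is produced, since the shells are not available, and that the eCRF holds examination findings as Protocol 8.2.2 states.

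**What to change.** **SAP 8.6.2.** Replace the first sentence with one stating that examination findings, with documented liver and spleen size, are listed for each subject at each visit and also summarized by visit and by dose. Keep the sentence on AEs.

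**SAP Section 9.** Replace the present entry with each departure that is kept and its reason:

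- Categorical laboratory results are listed and not shown as shifts, for the reason in SAP 8.6.7.
- Dose associations for the immune and vector parameters are descriptive only, read from the by-cohort tables. This needs declaring because Protocol 10.2.4.7 expected statistical methods.
- Hypoglycemic events are reported as subject counts by visit, with the reason; alternatively, restore the event counts by dose.

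If the sponsor prefers to leave examination findings to the AE tables alone, that too should be declared here with its reason.

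Pooled Dose 2 columns for the immune and vector tables are optional. They would combine three steroid regimens, and the cohort columns already identify dose.

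**Cost.** A few sentences of SAP text, one extra listing and one extra summary table, from findings that the protocol says are already captured.
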